6.3.4. Data Quality Assurance and Compliance

To ensure the highest quality of data capture across all sources, the Registry will implement the following quality assurance measures:

- **Automated Data Validation Checks**
Incoming data will be systematically screened for missing values, inconsistencies, and outliers at the point of entry using predefined validation rules aligned with international standards (ICD-10, SNOMED CT, LOINC).
- **Cross-Source Data Verification**
Clinical data extracted from EMRs will be compared against PROs to confirm consistency, with discrepancies flagged for review.
- **Audit Trails and Data Security**
All data modifications, including additions, corrections, or deletions, will be tracked through secure, HIPAA-compliant audit trails to ensure full traceability.
- **Regulatory Compliance**
All procedures will adhere to U.S. FDA and EMA guidelines for the use of RWE in regulatory decision-making, ensuring compliance with relevant national and international standards.
- **Periodic Reviews and Oversight**
The PI and designated data management personnel will perform regular reviews to assess adherence to protocol-defined quality benchmarks. The Registry's scientific steering

committee will also receive summary reports detailing data completeness, validation outcomes, and unresolved issues.

These layered measures will ensure the Registry produces accurate, reliable, and high-quality datasets suitable for robust observational research and regulatory submission.

6.4. Costs to the Participant and Payment for Participation

Participation in the Registry is voluntary, and participants will not incur direct costs for enrollment, data submission, or study-related activities. To acknowledge the time and effort required, the Registry will offer non-monetary engagement incentives, including entry into periodic randomized incentive distributions, designed to support retention without exerting undue influence or coercion.

6.4.1. No Direct Costs to Participants

Participants will not be charged for completing electronic surveys, EMR data retrieval, or other study-related activities. All Registry tasks, including PRO completion, EMR refreshes, and communications, are provided at no financial burden.

6.4.2. Participant Payment and Engagement Incentives

- Participation-Based Incentives:**

Participants who complete biannual PRO surveys and remain actively enrolled will be automatically entered into periodic incentive drawings. Specifically, gift card drawings will be conducted periodically for survey completion and active retention. Winners will be selected at random, and no additional steps are required beyond completing the associated activities.

- Non-Monetary Engagement Opportunities:**

Participants will have access to educational materials, aggregate study progress updates, invitations to webinars or virtual events, and optional certificates or badges recognizing their contributions to MPN research.

6.4.3. Potential Indirect Costs

Participants may require internet, smartphone, or computer access to complete study activities. While the Registry will minimize any institutional or medical record retrieval fees, these costs are not typically covered.

6.4.4. Payments from External Researchers for Data Access

The MPN Research Foundation may receive payments from approved external investigators who access de-identified data for secondary research. These funds will support Registry operations, improve data quality, and advance MPN research; they will not affect individual participant incentives.

6.4.5. Ethical Considerations and Regulatory Compliance

All compensation and incentive approaches comply with IRB, FDA, and EMA regulations. Participants will receive IRB-approved disclosures detailing drawing eligibility, prize distribution, data use, and external funding. Compensation is structured to ensure fair acknowledgment of participant contributions without coercion or undue influence.

7. METHODS AND PROCEDURES

Participation in the Registry consists of collection of the participants' information in a research database and the use of this information for observational research studies and for identification and recruitment of potential eligible participants for future research studies.

7.1. Data sources

Data collection for the registry will be done in non-interventional settings. This is not a clinical trial.

1. Registry participants may use a mobile and/or web-based application to add their participant-reported data (“Participant-Reported Data”).
2. Registry participants will be asked to provide their written informed consent for their health care providers to disclose relevant EMRs to MPN Research Foundation for inclusion in the Registry and for MPN Research Foundation to access EMRs directly using a medical records technology interface (“EMR Data” and together with PROs and Survey Data, “Registry Data”).
3. Registry participants will also provide information in response to surveys periodically administered by MPN Research Foundation (“Survey Data”).
4. Additional data may be generated from:
 - a. Medical claims and insurance data.
 - b. Mortality Data: Vital status and cause-specific mortality outcomes will be captured through linkage to national mortality datasets. This linkage will strengthen the accuracy of survival analyses, enhance longitudinal outcome assessments, and minimize loss to follow-up.
 - c. Data from affiliated disease registries.
5. The registry will collect a wide range of data variables, ensuring a holistic understanding of disease progression and treatment effects. These variables include:
 - a. **Demographics:** Age, sex, race, ancestral background, socioeconomic indicators, geographic location, history of military service, and insurance status.
 - b. **Clinical Data:** WHO-defined MPN subtype, disease stage, duration of disease, history of thrombotic events, splenomegaly, and systemic symptoms.
 - c. **Treatment Data:** Medication history, treatment response, adverse events, dose adjustments, and reason for therapy discontinuation.
 - d. **Genetic and Molecular Data:** JAK2, CALR, and MPL mutation status, variant allele frequencies, and other emerging genomic biomarkers.
 - e. **PROs:** Symptom burden assessment using MPN-SAF TSS, fatigue severity, psychological well-being, and functional status.
 - f. **Healthcare Utilization:** Frequency of hospitalizations, emergency department visits, specialist consultations, and treatment adherence.
 - g. **Environmental and Lifestyle Factors:** Tobacco use, alcohol consumption, dietary habits, physical activity, and occupational exposures.

6. PROs will be captured through structured survey instruments designed to measure symptom burden, quality of life, and treatment satisfaction. These surveys will include:
 - a. **MPN-SAF Total Symptom Score (TSS):** Assesses key MPN symptoms, including fatigue, pruritus, night sweats, bone pain, and early satiety.
 - b. **PGI-S:** Captures patient-perceived overall change in health status.
 - c. **EORTC QLQ-C30:** Evaluates overall health-related quality of life, including functional status and symptom burden.
 - d. **Modified PHQ-9:** Screens for depressive symptoms commonly observed in MPN patients.
 - e. **PROMIS Short Form v1.0 – Fatigue 8a:** Assesses fatigue in MPN patients, specifically targeting the experience of fatigue and its impact on daily life.
 - f. Data from patient surveys will be integrated with clinical and genomic data to create a robust dataset that allows for multidimensional analyses of disease progression, therapeutic impact, and patient experience.

In the future, participants may be invited to provide optional blood or tissue samples to support additional research on genetic, molecular, or biomarker analyses. Any biospecimen collection will require a separate IRB-approved protocol and additional informed consent. Participation in biospecimen sub-studies will be entirely voluntary and will not affect participation in the main registry.

7.2. Data Storage and Sharing

Data will be stored electronically within the MPN Research Foundation Service Database. Identifiable details, including names, email addresses, dates other than year, photographic images, and free-text notes, will be removed and replaced with a linkage code.

A designated Honest Broker for this study has been established with a third-party through a specific contractual agreement. Serving independently from the study analysis team and outside MPN Research Foundation, the Honest Broker will assign linkage codes, maintain the secure linkage file, and ensure the separation of identifiable data from research datasets. The linkage file will be stored in an encrypted system accessible only to the Honest Broker, with all access documented through audit trails. The Honest Broker will also serve as a resource to the MPN PROGRESSION Registry governance committees, including the Data Access, Use & Publications (DAUP) Committee.

Coded research data will be retained indefinitely by the MPN Research Foundation to support ongoing and future observational research, in accordance with organizational data retention policies and applicable regulatory requirements.

Investigator access to Registry data requires approval by the DAUP Committee, based on scientific quality, validity, and ethical compliance, with all approvals documented in writing. De-identified data may be shared with external researchers for approved secondary studies, subject to appropriate IRB approvals. Investigator access to Registry information for recruitment or eligibility screening will only occur with documented IRB approval.

While participants may receive insights from aggregate analyses, they will not necessarily be informed of all results from every observational study using their data.

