2. PURPOSE

The purposes of the MPN PROGRESSION Registry™ (“Registry”) are to:

- **Facilitate high-quality observational research** by collecting and analyzing EMRs, PROs, and linked external datasets — including mortality records, insurance claims, genetic testing results, and affiliated registries — to advance understanding of disease natural history, progression, real-world therapeutic effectiveness, and standards of care.
- **Improve clinical definitions of MPN disease progression** by incorporating updated diagnostic criteria and emerging biomarkers, ensuring refined characterization of pre-fibrotic myelofibrosis (pre-PMF), MPN in accelerated phase (MPN-AP), MPN in blast phase (MPN-BP) or post-MPN AML, and MDS/MPN overlap syndrome as defined above
- **Identify predictive biomarkers and surrogate endpoints** to support drug development, regulatory decision-making, and improved understanding of disease progression.
- **Enhance standards of care and patient outcomes** by leveraging RWE and longitudinal analytics to inform treatment sequencing, monitor therapeutic responses, and guide personalized care strategies.
- **Support participant identification for future research** by enabling review of Registry data to identify and contact individuals eligible for future studies conducted by the MPN Research Foundation or approved collaborators.

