4. OBJECTIVES

4.1. Primary Objectives

Stage 1: Feasibility Phase

The study will begin with a 12- to 24-month feasibility phase focused on participant retention, data completeness, EMR integration, and engagement strategies. Results from this phase will help optimize study operations, guide participant engagement, and inform potential protocol amendments.

- Evaluate enrollment feasibility and participant characteristics during the first 12–24 months.
- Characterize participant demographics, geographic distribution, and clinical settings.
- Assess inclusion of underrepresented populations to enhance the generalizability and heterogeneity of RWD.
- Assess representativeness of enrolled participants relative to the broader U.S. MPN population, ensuring alignment with clinical and demographic patterns.
- Determine the proportion of participants providing a Minimal Viable Dataset (MVD) at enrollment.
- Monitor consent rates for longitudinal EMR access and secondary data use.
- Identify gaps in baseline data completeness and develop strategies to mitigate missing information.
- Track participant retention at 12, 18, 24, and 36 months, and evaluate completion of at least three consecutive follow-ups.
- Identify early indicators of dropout or disengagement to inform retention strategies.
- Monitor response rates to quarterly PRO surveys (e.g., MPN-SAF TSS, PROMIS Short Form v1.0 – Fatigue 8a) and evaluate follow-up strategies (automated vs. manual).
- Assess the proportion of participants using secondary contacts (caregivers, clinicians) for follow-up.
- Measure success rates of EMR integration across sites using FHIR-based interoperability, compare self-reported and EMR-extracted data, and validate processing scalability.

Stage 2: Surrogate Endpoint Phase

- Establish composite surrogate endpoints integrating genetic markers (e.g., variant allele frequency shifts), clinical indicators (e.g., fibrosis progression, cytopenias), inflammatory markers (e.g., cytokine levels), and PROs (e.g., MPN-SAF TSS, PROMIS trends).
- Ensure surrogate endpoints align with FDA and EMA regulatory standards for clinical trials.
- Incorporate RWD (EMR, claims, PROs) to validate surrogate markers of disease progression.
- Determine time from baseline to first progression event (e.g., ET → PV → MF, blast phase transformation) and assess median time to progression by subtype.
- Measure progression rates per WHO 2022/IWG-MRT criteria using updated risk stratification models.

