6.1. Duration of Observation and Participation

Participants will be followed for a minimum of five years, with the potential for extended participation beyond ten years to support long-term observational analyses.

Standardized data collection will occur at baseline, six months, and every six months thereafter. Collected data will include:

- EMR extractions (clinical history, labs, imaging, treatments)
- Insurance claims and pharmacy records (healthcare utilization, medication use)
- PROs, including MPN- SAF TSS, PROMIS Short Form v1.0 – Fatigue 8a, and quality-of-life assessments

Data integration will prioritize FHIR-based EMR retrieval, supplemented by validated participant surveys and secondary data sources.

Ongoing monitoring and planned assessments include:

- **Year 1:** Baseline validation, data completeness review, and participant engagement check
- **Year 3:** Disease trajectory modeling, retention analysis, and interim outcome assessment
- **Year 5 and beyond:** Predictive analytics on disease progression, long-term outcomes, and composite endpoint evaluation

To promote retention, the Registry will deploy automated reminders, provide quarterly study updates, and offer virtual engagement opportunities (e.g., newsletters, webinars). Participants may withdraw at any time, as outlined in Section 6.2.

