6.3.1. Data Collection Intervals and Structured Follow-Up Schedule

Participants will be followed for a minimum of five years, with many continuing beyond ten years.

| Follow-Up | Data Collected | Collection Method |
|-----------|----------------|-------------------|
|-----------|----------------|-------------------|

| Timepoint | | |
|----------------------------|---|---|
| Baseline (Enrollment) | Demographics, medical history, WHO 2022 MPN subtype, other hematologic disease information (e.g., post-MPN AML, MDS/MPN overlap syndrome as defined above, history of SCT and/or BMT) baseline labs, molecular testing (if available), treatment history, and PROs (MPN-SAF TSS, EORTC QLQ-C30, modified PHQ-9, PGI-S, PROMIS Short Form v1.0 – Fatigue 8a) | Initial EMR extraction, PROs, insurance claims |
| Every 3 Months (0-10+ yrs) | Symptom burden updates (MPN-SAF TSS + PGI-S) | PROs |
| Every 6 Months (0-10+ yrs) | Updates on disease status, treatment changes, adverse events, healthcare utilization, molecular/genetics results (if available), mortality status, progression milestones, and PROs (MPN-SAF TSS, EORTC QLQ-C30, modified PHQ-9, PROMIS Short Form v1.0 – Fatigue 8a) | EMR reauthorization, PROs, claims retrieval, mortality data linkage |

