9.1 Statistical Analysis Plan (SAP)

An initial SAP will be developed prior to data collection, outlining intended descriptive and inferential statistical methods, including Kaplan-Meier survival analysis²⁶, Cox proportional hazards modeling²⁷ for progression events, and multivariate analyses. Primary endpoints include time to documented MPN progression events and overall survival. Secondary endpoints include PROs, quality-of-life measures (e.g., EORTC QLQ-C30), and healthcare utilization patterns. Overall survival and cause-specific mortality endpoints will be determined using EMR data and validated through linkage with national mortality datasets, ensuring robust and comprehensive survival analyses. The SAP will undergo formal annual reviews and be updated based on interim analysis results, changes in data availability, or emerging scientific questions. Significant amendments will be documented, scientifically justified, and communicated to the IRB. Data will be securely retained for a minimum of 10 years following study completion, in accordance with institutional policies and regulatory requirements.

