9.5 Competing Risks and Time-dependent Covariate Analyses

Competing risk analyses, such as Fine and Gray's subdistribution hazard models²⁹, will be utilized to appropriately account for events that might prevent or alter the probability of the primary outcomes, ensuring unbiased estimates of progression risk. Additionally, time-dependent covariate analyses will evaluate how changes in treatment regimens, symptom severity, or other relevant covariates over time influence disease progression or outcomes.

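### Section 7.2 keeps only the year of each date in the coded data and no section retains study days, so individual event times and within-year order are lost to the planned time-to-event analyses

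*Protocol*

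**What the plan says.** **The rule.** Protocol Section 7.2 states: "Identifiable details, including names, email addresses, dates other than year, photographic images, and free-text notes, will be removed and replaced with a linkage code". The Honest Broker, who is independent of the analysis team, must also "ensure the separation of identifiable data from research datasets" and alone can open the linkage file. Section 8.1 repeats that separation.

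**What the data are for.** Section 9.1: "Primary endpoints include time to documented MPN progression events and overall survival", with Kaplan-Meier and Cox methods named. Stage 2 in Section 4.1 aims to measure time from baseline to first progression and to "assess median time to progression by subtype". Section 9.5 plans that "time-dependent covariate analyses will evaluate how changes in treatment regimens, symptom severity, or other relevant covariates over time influence disease progression". Section 2 wants the registry to "inform treatment sequencing, monitor therapeutic responses".

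**What timing might survive.** Section 6.1: "Standardized data collection will occur at baseline, six months, and every six months thereafter". The six-monthly row in Section 6.3.1 covers "Updates on disease status, treatment changes, adverse events, healthcare utilization, molecular/genetics results (if available), mortality status, progression milestones". MPN-SAF TSS and PGI-S are collected every three months. Section 7.1 lists disease duration as a clinical variable, with no unit or resolution. No section says that study days, elapsed times, shifted dates or wave labels are held in the coded data.

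**The concern.** Time-to-event analysis uses intervals and order, and Section 7.2 removes what both are computed from. Dates are available at finer resolution before the rule applies: the pre-screening form in Section 10.6 asks for month and year of diagnosis. The loss therefore comes from the coding rule and not from the source.

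Two things are at stake. First, each participant's time to progression or death is known only as a difference of calendar years. Second, when treatment start or a marker change falls in the same year as progression, the analyst cannot tell which came first. A time-dependent covariate analysis depends on that order. The second loss is the more serious, because no choice of model brings the order back.

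**Working it through.** The protocol gives no figure for this loss, so there is none to reproduce. The following are assumptions that the protocol does not state: dates uniform within the calendar year; exponential times; and, where a progression rate is needed, 50% by 5 years. Table 1 assumes 50% progression over a follow-up of unstated length; five years is the minimum follow-up in Section 6.1.

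**1. Error in one interval.** Let u be the start date as a fraction of its year and t the true time. The recorded value is floor(u + t). If f is the fractional part of t, the error is −f with probability 1 − f, and 1 − f with probability f. Its mean is 0 and its variance f(1 − f). Averaged over f this is 1/6, so SD = √(1/6) = 0.408 years = 4.9 months. The share off by more than 6 months is 2∫₀^0.5 f df = 0.25. Simulation with exponential times (mean 5 years) gives the same 0.408 and 0.250.

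**2. Events at time zero.** With hazard L, the chance of a recorded value above 0 is S(0) = (1 − e^−L)/L. For L = ln 2/5 = 0.1386, S(0) = 0.934. The share of 5-year progressions recorded at time 0 is 0.066/0.50, or about 13%.

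**3. Kaplan-Meier on year differences.** S(1) = e^−L · S(0). The curve reads a median of 1 year when S(0) > 0.5 ≥ S(1), which holds for every true median from 5.2 to 17.8 months. For a true median of 6 months (L = 1.386), 1 − S(0) = 45.9% of events fall at time 0; for 12 months (L = 0.693), 27.9%.

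**4. Interval-censored Weibull on the same year-only data** (n = 200, 200 replicates):

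| True median (months) | Mean estimate | SD |
|---|---|---|
| 6 | 6.0 | 0.7 |
| 9 | 9.0 | 0.9 |
| 12 | 11.9 | 1.1 |
| 15 | 15.2 | 1.3 |
| 60 | 60.7 | 5.3 |

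The median is therefore estimable if the model holds.

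**5. Order of two events.** Events g months apart share a calendar year with probability 1 − g/12: 92%, 75%, 50% and 25% for 1, 3, 6 and 9 months. They share a 6-month wave with probability 1 − g/6: 83% and 50% for 1 and 3 months. Next, assume treatment starts at 0.2 per year before progression and at 0.5, 1 or 2 per year after it. Among progressors with a treatment record, the order is unknown in:

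| Timing retained | 0.5/y | 1/y | 2/y |
|---|---|---|---|
| Year only | 24% | 33% | 45% |
| 6-month wave label | 14% | 19% | 29% |
| Wave label and year | 11% | 16% | 25% |
| Wave label, 20% of refreshes missed | 19% | 26% | 36% |

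**6. Effect on a time-dependent hazard ratio** (simulated Cox models, N = 1500 for the treatment effect).
- True HR 1.0, same-interval treatment counted as first: 1.4 to 3.8 year-only, 1.2 to 2.6 with waves.
- True HR 1.0, exposure lagged one interval: 0.99 to 1.00.
- A lasting HR of 0.70 under a one-year lag: 0.70 to 0.76.
- A marker assumed to triple the hazard for 6 or 12 months, lagged: 1.2 or 1.7 year-only, 1.8 or 2.5 with waves, 3.0 with exact dates.

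**7. Fixed marker** (N = 1500, prevalence 20%, true HR 1.3): 1.304 with exact dates, year-only dates and waves alike.

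**The case against.** The strongest reply is that this argues from silence. Section 7.2 removes dates; elapsed days and wave labels are not on its list. Nothing says that full dates are destroyed, and nothing stops the Honest Broker or another authorised party from deriving intervals before release. A SAP or data-management plan not shown here may provide for it. The protocol never promises month-level resolution, and it schedules progression and treatment updates only every six months. Symptom scores, one of the time-varying covariates named in Section 9.5, come every three months.

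Much of this stands. A reader might infer that median time to progression by subtype cannot be resolved below one year. Step 4 shows otherwise: that limit belongs to Kaplan-Meier on year differences, and a SAP could choose another estimator. A reader might also infer that treatment effects will be badly biased. The hazard ratios of 1.4 to 3.8 need assumed treatment rates and an analyst who counts same-year exposure as first; a lag removes the bias. Nor is the risk-marker power in Table 1 undermined, as step 7 shows.

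What does not stand is that the rule is harmless. It is a stated rule, not an omitted detail, and the protocol that contains it makes no provision for relative times. A parametric fit returns a median, not individual times or event order. Wave labels help only if kept, widen when a refresh is missed, and leave the historical data in Section 3 at year resolution.

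**Conclusion.** The point holds in limited form. Section 7.2 as written conflicts with the protocol's time-to-event endpoints and time-dependent analyses. Individual times are known to the calendar year (error SD 4.9 months, a quarter off by more than 6 months), and the named Kaplan-Meier analysis becomes very coarse for any subtype with a short median. The protocol gives no subtype medians, so whether that range matters is unknown.

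The lasting loss is order within a year, above all before enrolment. Lagging exposure protects against bias but weakens effects that act over months. The ordering percentages and the size of that weakening rest on assumed rates and show scale only; the error SD rests only on uniform dates and smoothly spread times.

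This should be fixed, but it does not invalidate the registry. Source dates may well survive outside the research dataset, so the gap can be closed.

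**What to change.** Amend Section 7.2 to say that, before calendar dates are removed, every clinical, treatment, PRO and death date, including those before enrolment, is converted to days from enrolment, or given one fixed shift per participant that preserves all intervals. The Honest Broker or another party with authorised access to dates should do this. State that the coded dataset keeps these intervals, the enrolment year and the 3-month and 6-month collection-wave labels. Interval error from coding then falls to zero, and the order of dated events is preserved to the resolution of the source.

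The cost is protocol and data-management wording plus one derivation step. That step may have to be added to the Honest Broker's duties, which Section 7.2 describes as assigning codes, holding the linkage file and separating identifiers. Re-identification risk rises somewhat compared with year-only data, which matters because Section 8.1 already flags linkage to external registries. No further participants or procedures are needed.
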